- a. All subjects will be followed up for response until 12 months after the last subject has stopped RT/CRT, or earlier due to any reason whereby tumor assessments are no longer applicable (e.g., if a new treatment is started, withdrawal of consent). The reason for early discontinuation should be captured in the source document. If EOT occurs before PTD 365, all assessments must be done as planned for PTD 365. After completing the PTD 365 visit, subjects will be followed up for survival via phone call every 3 months, wherever possible.
- b. RT to be given 1.5 hours (\pm 30 minutes) after dosing.
- c. FD10 is the day of the last dose of RT. In case of premature withdrawal from the trial during the treatment period, the investigations scheduled for the visit on FD10 should be performed. In such cases this visit will be considered the Early Treatment Termination visit. If FD10 is on a Friday, PK, PD, safety laboratory, and urinalysis sampling must be done on FD9.
- d. All AEs will be collected from FD1 up to PTD 21 to evaluate the occurrence of DLTs.
- e. Hepatitis B and C testing to be performed at Screening unless obtained within 3 months prior to Screening. Screening for HIV will be performed according to local practice and local regulatory guidance.
- f. Heart rate, diastolic and systolic blood pressure, body temperature, and body weight. See Section [7.4.4](#) for details.
- g. Height measured at Screening only.
- h. Only required if subject has not started a new antitumor treatment. If a new treatment is started, the date (and regimen) must be reported in the eCRF.
- i. Physical exam will report findings in the irradiated area during all FU periods.
- j. Evaluation of ongoing treatment-emergent adverse events.
- k. See [Table 15](#) for details of hematology tests.
- l. See [Table 15](#) for details of serum chemistry tests.
- m. Urinalysis: dipstick followed by microscopic examination if abnormal results.
- n. 12-lead resting ECG in triplicate.
- o. 12-lead ECG to be performed predose and once at 2 to 3 hours postdose.
- p. 12-lead ECG to be performed at 2 hours postdose.
- q. Tumor imaging by CT or MRI at baseline to document extent of lesions according to RECIST v1.1. Baseline tumor evaluation can be up to 28 days old when treatment starts.

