- r. Tumor assessments to be done at long-term safety FU (every 6 weeks during Day 31-180 [4 assessments]) and during survival FU (every 13 weeks during Day 181-365 [2 assessments]). Tumor assessment will not be repeated on PTD 180.
- s. PK samples will be collected as detailed in [Table 9](#). Sampling schedule may be changed by the SMC based on emerging data. See Section [7.5.1](#) for details.
- t. Predose only.
- u. Mandatory archival tumor materials sampled before start of the treatment (most recent materials available). If no archival tumor material is available a fresh biopsy must be taken.

CCI

- x. PTD 210 and 312 will consist of phone calls to evaluate long term RT toxicity. No other assessments will be performed at these visits.
- y. Can be followed up via phone call every 3 months.

Table 2 Schedule of Assessments – Phase Ia (Arm A): Tablet Cohorts

Trial Periods	Screening	DLT Evaluation Period					Short-term Safety FU	Mid-term Safety FU	Long-term Safety FU	Survival FU/EOT ^a
		Treatment Period (M3814 + RT)			DLT Period					
Trial Days	Day -21 to Day -1	FD 1 to FD 10			PTD 1 to 21	PTD 22 to 30	PTD 1 to 90	PTD 31 to 365	PTD 181 to 365	
M3814 Tablet ^y	-	X		X						-
M3814 Capsule			X							
RT 3 Gy x 10 (5 F/W) ^b	-	X								-
Visit Days	-21 to -1	FD1	FD2	FD6 ^z	FD7	FD10 ^c /ETT	PTD 8, 15	PTD 22 ^d , 30	PTD 84	PTD 42, 126, 168, 180, 210 ^{aa} , and 312 ^{aa}
Visit Window (days)	-	-		-		-	±2	±2	±7	±7
Signed informed consent	X									
Inclusion/exclusion criteria	X	X								
Demography	X									
Medical history	X									
Serum β-HCG pregnancy test (if applicable)	X						PTD 30 only			
Infection screen (hepatitis B and C), optional HIV test ^e	X									
Vital signs ^f	X ^g	X		X		X	X	X	X	X ^h
Physical examination	X	X		X		X	X	X	X	X ⁱ
Clinical examination of bleeding	X	X		X		X	X			

Trial Periods	Screening	DLT Evaluation Period					Short-term Safety FU	Mid-term Safety FU	Long-term Safety FU	Survival FU/EOT ^a
		Treatment Period (M3814 + RT)			DLT Period					
Trial Days	Day -21 to Day -1	FD 1 to FD 10			PTD 1 to 21	PTD 22 to 30	PTD 1 to 90	PTD 31 to 365	PTD 181 to 365	
M3814 Tablet ^y	-	X		X						-
M3814 Capsule			X							
RT 3 Gy x 10 (5 F/W) ^b	-	X								-
Visit Days	-21 to -1	FD1	FD2	FD6 ^z	FD7	FD10 ^c / ETT	PTD 8, 15	PTD 22 ^d , 30	PTD 84	PTD 42, 126, 168, 180, 210 ^{aa} , and 312 ^{aa}
Visit Window (days)	-	-		-		-	±2	±2	±7	±7
Esophageal endoscopy (if relevant)	X									
Evaluation of all tissues in RT area				X		X	X	X	X	X

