6.1 Secondary safety analysis

Cut-off date:

This IAP covers the analyses for efficacy and safety based on the data cut-off (see also chapter 9 Data handling after cut-off date). Statistical analyses will be performed using cleaned eCRF data gained up to a clinical cut-off date which is determined when last subject has reached the second post-treatment tumor assessment.

The cut-off date is determined once a data extract (before data base lock) is available which indicates that the last subject has reached the second post-treatment tumor assessment. The clinical cut-off date will be the date on which according to this data extract the last subject has reached the second post-treatment tumor assessment.

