Mean, Min, Median, Max, GeoMean, 95% CI: 3 significant digits

SD: 4 significant digits

CV%, GeoCV%: 1 decimal place

Definition of baseline:

The last measurement prior to first administration of trial treatment (either M3814, RT or Cisplatin) will be used as the baseline measurement.

Definition of treatment day:

Treatment Day 1 is defined as the date of first administration of trial treatment (M3814 and/or RT and/or Cisplatin), the day before is defined as Treatment Day –1 (no Treatment Day 0 is defined).

Definition of on-treatment evaluations for safety analyses:

On-treatment evaluations for safety analyses will be evaluations performed on or after Treatment Day 1 until 30 days after the last dose of trial treatment or the clinical cut-off date (if the treatment is still ongoing).

Definition of duration:

Duration will be calculated by the difference of start and stop date + 1 (e.g. survival time (days) = date of death – date of first dose + 1), if not otherwise specified.

Conversion factors:

The following conversion factors will be used to convert days into months or years:
1 month = 30.4375 days, 1 year = 365.25 days.

Data handling after cut-off date:

Data after cut-off do not undergo the cleaning process. The only exceptions are the date of death and the date last known to be alive. Data obtained after the cut-off will not be displayed in any listings or used for summary statistics (e.g. laboratory values of samples taken after data cut-off, AE with onset date after data cut-off, etc.) will not be included in any analysis or listing.

For any adverse event or concomitant medication starting before the cut-off date, the end date will not be imputed (even if the end date is after the cut-off date) and will be presented as filled in the eCRF at the time of the data export.

Handling of missing data:

For identification of AE treatment emergence, incomplete dates will be handled as follows:

- In case the onset date is completely missing or the onset is in the same year (if the onset year is available only) or the onset is in the same month and year (if the day is missing) as start of trial treatment then the onset date will be replaced by the minimum of start trial treatment and AE resolution date.

- In all other cases, the missing onset day or onset month will be replaced by 1.

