14.1 Best Overall Response

Population: FAS Analysis Set

The Best Overall Response (BOR) will be defined as the best response per RECIST 1.1 across all time points until determination of Progressive Disease (PD) or cut-off date, using the Investigator reported overall response per time point and excluding assessments after tumor surgery.

BOR will be defined as the best response across all time points (for example, a subject who has stable disease (SD) at the first assessment, partial response (PR) at the second assessment, and PD at the last assessment has a BOR of PR). The order to obtain the BOR is the following: complete response (CR), Partial Response (PR), Stable Disease (SD), Progressive Disease (PD), Not Evaluable (NE).

When SD is believed to be the best response, it must also meet the protocol-specified minimum 6 weeks (42 days) from first day of treatment. If the minimum time is not met, the subject's best overall response depends on the subsequent assessments. For example, a subject who has SD at the first assessment, PD at the second assessment and does not meet the minimum duration for SD, will have a best overall response of PD. The same subject lost to follow-up after the first SD assessment would be considered NE for BOR.

If a subject has missing baseline tumor assessment and/or no tumor assessment on-treatment, BOR will be NE.

The confirmed BOR will be also analyzed. In this case, CR and PR need to be confirmed at a subsequent assessment, at least 4 weeks after initial overall response assessment of CR/PR. Confirmed BOR will be derived as described in RECIST 1.1 guidance.

Overall response first time point	Overall response subsequent time point*	Confirmed BOR
CR	CR	CR
CR	PR	SD, PD or PR ^a
CR	SD	SD, if minimum criteria for SD duration met at first time point. Otherwise PD
CR	PD	SD, if minimum criteria for SD duration met at first time point. Otherwise PD
CR	NE	SD, if minimum criteria for SD duration met at first time point. Otherwise NE
PR	CR	PR
PR	PR	PR
PR	SD	SD
PR	PD	SD, if minimum criteria for SD duration met. Otherwise PD
PR	NE	SD, if minimum criteria for SD duration met. Otherwise NE
NE	NE	NE

* Subsequent time point is not necessarily the direct subsequent scan (eg. PR-SD-PR will have PR as confirmed BOR)

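### SAP 14.1 makes best overall response non-evaluable without an on-treatment scan, though none is scheduled, and excludes later scans only after tumor surgery, not after new drug therapy or radiotherapy

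*SAP*

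**What the plan says.** SAP 14.1 defines BOR as "the best response per RECIST 1.1 across all time points until determination of Progressive Disease (PD) or cut-off date". On which assessments enter the derivation, the section specifies: "using the Investigator reported overall response per time point and excluding assessments after tumor surgery". A later paragraph adds the NE rule: "If a subject has missing baseline tumor assessment and/or no tumor assessment on-treatment, BOR will be NE". ORR and DCR, with exact confidence intervals, are built on BOR, in unconfirmed and confirmed form.

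The SAP defines on-treatment once, in section 9, under a heading that limits it to safety analyses: "evaluations performed on or after Treatment Day 1 until 30 days after the last dose of trial treatment". For subjects still being treated, the window closes at the data cut-off instead. No definition is given for efficacy. SAP 6.1 sets its data cut-off when "the last subject has reached the second post-treatment tumor assessment", so it labels the same scans as post-treatment.

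Footnote r to Protocol Table 1 (Phase Ia Arm A, capsule) gives the first part of the schedule: "Tumor assessments to be done at long-term safety FU (every 6 weeks during Day 31-180 [4 assessments"]. For the later scans the same footnote has: "during survival FU (every 13 weeks during Day 181-365 [2 assessments"]. Tables 2 (Arm A, tablet) and 5 (Arm B) follow the same timing.

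Footnote a to the same tables ends response follow-up at a fixed time or "earlier due to any reason whereby tumor assessments are no longer applicable (e.g., if a new treatment is started, withdrawal of consent"). Protocol 7.1.3.5 makes tumor assessments mandatory only while no new antitumor treatment has begun, and asks for the new treatment's date and regimen in the eCRF. Protocol 6.6.2 bars other anticancer therapy until 30 days after radiotherapy. SAP 12.5 lists subsequent drugs, surgery and radiotherapy but does not connect them to BOR.

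**The concern.** There are two separate faults in one section.

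**The NE rule.** It requires an on-treatment scan in a trial whose response scans all come after treatment. A programmer who applies the only available window would set BOR to NE for every subject on the regular schedule. The exceptions would be subjects with an unscheduled scan or an early End of Trial visit, since an early End of Trial triggers the full PTD 365 assessments, tumor assessment included. Subjects who left early could then be evaluable while those who followed the schedule would not.

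**The exclusion rule.** By dropping scans after tumor surgery, the SAP accepts that response after another anticancer intervention should not be credited to trial treatment. It gives no reason for leaving out drug therapy and radiotherapy. The protocol's stop at new treatment is not carried into the derivation.

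At stake are the endpoints for the Phase Ia antitumor-activity objective. A response to later therapy could be attributed to M3814 with RT or CRT. Escalation cohorts have 3 subjects, so one misattributed response moves a cohort's ORR by 1/3, or 33 percentage points.

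**Working it through.** **Inputs**
- Follow-up scan visits, all ±7 days: PTD 42, 84, 126, 168, 270 and 365 (Protocol Tables 1, 2 and 5).
- On-treatment window: to last dose + 30 days (SAP 9).
- Ban on other anticancer therapy: to 30 days after RT (Protocol 6.6.2).
- Fractions, 5 per week: 10 in Arm A, 33 to 35 in Arm B.
- PTD counts from the end of the treatment period (notes to the schedule tables).

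**Reproducing the stated scan counts.** PTD 42, 84, 126 and 168 lie in Day 31-180, giving 4. PTD 270 and 365 lie in Day 181-365, giving 2. The total is 6, as the footnote says.

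**Scans inside the on-treatment window**

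| Visit (PTD) | Earliest (−7) | By PTD 30? |
|---|---|---|
| 42 | 35 | No |
| 84 | 77 | No |
| 126 | 119 | No |
| 168 | 161 | No |
| 270 | 263 | No |
| 365 | 358 | No |

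This gives 0 of 6. The gap from window end to first scan runs from 35 − 30 = 5 days to 49 − 30 = 19 days. The visits up to PTD 30 list no tumor assessment (Protocol 7.1.3.1 to 7.1.3.3).

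**In calendar days, Monday start, no delay**
- Arm A: the last fraction is Day 12. The window ends on Day 12 + 30 = 42. The first scan is between Day 12 + 35 = 47 and Day 12 + 49 = 61.
- Arm B: the last fraction is Day 45 (33 fractions) to Day 47 (35 fractions). The window ends on Day 75 to 77. The first scan is between Day 45 + 35 = 80 and Day 47 + 49 = 96.

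Other start days, or RT delays, move the last dose and the PTD origin together, so the 5-day minimum gap stays.

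**What the literal rule produces.** With only scheduled scans, ORR = 0/n. At n = 30, used as an illustration because it is the escalation cap per arm, the exact 95% upper limit is 1 − 0.025^(1/30) = 11.6%, so the result would read 0% (0 to 11.6%) whatever the scans showed.

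**Exposure to new therapy**
- From PTD 31, when the ban has ended, to the first scan: 35 − 31 = 4 to 49 − 31 = 18 days. New therapy can therefore precede any of the 6 scheduled scans.
- From a PTD 42 response to a confirming scan at PTD 84: (84 − 7) − (42 + 7) = 28 to (84 + 7) − (42 − 7) = 56 days. Therapy started in that interval would not block confirmation.

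The documents give no rate of subsequent therapy before progression, so the effect on ORR cannot be computed.

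**The case against.** **On the NE rule.** The section 9 window is labelled for safety, while BOR is an efficacy analysis. Section 14.1 speaks of all time points and works an example over three successive scans. It also requires stable disease to last at least 42 days from first treatment, which a window ending on Day 42 in Arm A would hardly allow. A careful reader would infer 'post-baseline'. This stands as evidence of intent, but it does not make the sentence correct. Elsewhere the SAP treats on-treatment and post-treatment as distinct periods: late toxicities (15.2.3) begin after the on-treatment period, and the laboratory section (15.4) sets the worst grade to missing when there is no on-treatment evaluation. Reusing that flag for BOR would be a reasonable programming choice.

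**On the count of 0 of 6.** A one-week cisplatin delay is allowed. With 33 fractions and a Monday start, the FD31 dose could move from Day 43 to Day 50 and the window end to Day 80, which is also Day 45 + 35 if PTD runs from the last RT fraction. That only touches the boundary, and it disappears if PTD runs from the end of all trial treatment.

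**On new therapy.** The protocol does not require scans after new treatment, investigational agents are barred throughout, and imaging dates and later therapy are both listed by subject. Few such scans may exist. That the protocol's stop is there to prevent misattribution is an inference, since no passage gives its purpose. All of this bears on frequency. None of it bars the scans, and 14.1 would count them.

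**Conclusion.** Both parts hold and should be corrected.

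The NE sentence is wrong as written: none of the 6 scheduled post-baseline scans falls in the only on-treatment window the SAP defines, and outside that window the term has no stated meaning for efficacy. Its practical effect depends on whether the programmer follows the sentence or the evident intent.

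The exclusion rule is incomplete. It can credit later drug therapy or radiotherapy to trial treatment, through a first response or through a confirming scan. Its size is unknown.

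The consequence is limited to descriptive secondary endpoints; the DLT analysis does not change. The calendar days assume a Monday start and no missed fractions. The minimum 5-day gap assumes that PTD is counted from the last dose of trial treatment.

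**What to change.** Make two changes in SAP 14.1.

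1. In the NE rule, replace the on-treatment condition with: *no evaluable post-baseline tumor assessment on or before first PD, before the start of subsequent anticancer therapy and by the cut-off date*. Progression at the first scan then remains PD.
2. Widen the exclusion to: *excluding assessments after the start of any subsequent anticancer drug therapy, radiotherapy or tumor surgery*. Take the start dates from the existing after-discontinuation eCRF pages named in SAP 12.5.

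Apply the filter to unconfirmed and confirmed BOR (including the confirming scan), ORR, DCR, and the spider and waterfall plots. Keep every scan in the listing.

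The cost is two sentences and one date filter. No new data are needed: the protocol already asks for the date of a new treatment, and SAP 14.1 already reads post-treatment drug therapy dates to find the last date known alive. The downside is that a few more subjects may be classed as NE. The filter would also drop scans taken after later radiotherapy to another site; if the sponsor wants to keep those, the SAP should say so explicitly.

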15.1 DLT (Primary endpoint)

Population: DE Analysis Set

A table with a summary DLTs during the DLT period, as confirmed by the SMC, will be provided for each dose level and overall with:

- Number of subjects with no DLT
- Number of subjects with DLT: one DLT, at least two DLTs

The listing of all DLTs (identified either by Investigator or by SMC) will also be provided.

15.2 Adverse Events

All TEAEs will be summarized, i.e. those events that are emergent during treatment having been absent pre-treatment, or worsen relative to the pre-treatment state and with onset dates occurring within the first dosing day of trial treatment until 30 days after the last dose of trial treatment. If an adverse event started before treatment start and improved during treatment (i.e. with the same PT directly following, but lower grade) it should not be counted as a TEAE. However, if an adverse event started either before or during the treatment period and worsened during the treatment period this should be reported as a TEAE.

Counting rules and observation periods for AEs during the treatment period (TEAEs):

- The treatment period is defined from the first dosing day of trial treatment until 30 days after the last dose of trial treatment or the clinical cut-off date.
- If an AE is reported for a given subject more than once during treatment, the worst severity and the worst relationship to trial treatment will be tabulated.
- Adverse events related to trial treatment are those events with relationship missing, unknown or related to at least one treatment (M3814, RT or Cisplatin).
- Adverse events related to M3814 are those events related to M3814, regardless to relationship with RT and/or Cisplatin

- Adverse events related to RT are those events related to RT, regardless to relationship with M3814 and/or Cisplatin
- Adverse events related to Cisplatin are those events related to M3814, regardless to relationship with M3814 and/or RT
- In case a subject has events with missing and non-missing grades, the maximum of the non-missing grades will be displayed.

For identification of AE treatment emergence, incomplete dates will be handled using the rules presented in section 9.

AEs will be coded according to the current MedDRA. The severity of AEs will be graded using National Cancer Institute - Common Terminology Criteria for Adverse Events (NCI-CTCAE) version 4.03 toxicity grades.

